
5.2 Exclusion Criteria
	
Replacement
	
2. Previous participation in a clinical trial evaluating a modified rFVIIa agent (including rFVIIa biosimilars, SC rFVIIa, PEGylated rFVIIa, NN1731, BAY86-6150, LR769, rVIIa-FP (CSL689), MOD-5014). Note: IV use of NovoSeven® is not an exclusion criteria.
 
With:
 
2. Previous participation in a trial involving Subcutaneous Administration of rFVIIa (Novo Seven or MOD-5014) or any trial using a modified rFVIIa such as: NN1731 or BAY86-6150. Prior participation in a trial of LR769 or rFVIIa-FP (CSL689) is permissible.

8.2 Study Procedures
	
Deletion
	
Diary entry of PRO scales at Part 1a Pre-dose

8.2 Study Procedures
	
Deletion
	
7 hr post-specimen draws at Day 3 and 5: MarzAA antigen and activity levels, as well as coagulation parameters, will be measured during Part 2 of the study at Day 1 (At pre-dose and Hour 7 post-dose, Day 3 (Pre-dose and Post-dose

CONFIDENTIAL CATALYST BIOSCIENCES, INC.

6

25 August 2018

MAA-201 VERSION 2.0

		Hour 7), Day 5 (Pre-dose and Post-dose Hour 7), Day 7 (Pre-dose and Post-dose Hour 7).
8.2.2.1 Pre-dose evaluations	Deletion	Immunogenicity assays to FVII, FVIIa, and MarzAA at Part 1a Pre-dose
8.2.2.1 Pre-dose evaluations	Deletion	Diary entry of PRO scales (see Appendix B – EQ-5D, VAS; Haem-A-QoL; HAL)
APPENDIX B	Updating	Link to HAEM A QoL
APPENDIX C	Deletion	Diary entry of PRO scales at Pre-dose at Part 1a Pre-dose
APPENDIX C	Deletion	Immunogenicity assays to FVII, FVIIa, and MarzAA at Part 1a Pre-dose

Administrative changes: Minor changes involving grammar, wordsmithing, punctuation, and other editorial changes have been made throughout the document. All are clearly identified in the track-changes version of the amendment.

MAA-201 VERSION 2.0

ABBREVIATIONS

ABR	Annualized bleeding rate
ADL	Activities of daily living
AE	Adverse event
AICC	Anti-inhibitor coagulant complex
ALT	Alanine aminotransferase
APCC	Activated prothrombin complex concentrates
aPTT	Activated partial thromboplastin time
AST	Aspartate aminotransferase
AUC	Area under the curve
BMI	Body mass index
BU	Bethesda Units
BUN	Blood urea nitrogen
CAD	Coronary artery disease
CBC	Complete blood count
CD4	Cluster of differentiation 4
CFR	Code of Federal Regulations
ClinRO	Clinician reported outcomes
Cmax	Concentration maximum
CMP	Clinical Monitoring Plan
CNS	Central nervous system
Cr	Creatinine
CRF	Case report form
DCC	Data Coordinating Center
DHHS	Department of Health and Human Services
DNA	Deoxyribonucleic acid
DSMB	Data Safety Monitoring Board
DVT	Deep venous thrombosis
EC	Ethics Committee
ECG	Electrocardiogram
EDC	Electronic Data Capture

MAA-201 VERSION 2.0

EQAS	External quality assessment scheme
eCRF	Electronic Case Report Forms
EQ-5D	European Quality of Life-5 Dimensions
F1+2	Prothrombin fragment 1+2
FVII	Factor VII
FVIIa	Factor VII activated
FVIII	Factor VIII
FIX	Factor IX
FDA	Food and Drug Administration
GCP	Good Clinical Practice
GIT	Gastrointestinal Tract
GLP	Good Laboratory Practices
GMP	Good Manufacturing Practices
GS	Gilbert's syndrome
GWAS	Genome-Wide Association Studies
H0	Null hypothesis
H1	Alternative hypothesis
Haem-A-QoL	Hemophilia A quality of life questionnaire
HAL	Hemophilia Activities List
HIPAA	U.S. Health Insurance Portability and Accountability Act
Hr	Hour
HTC	Hemophilia Treatment Centre
IB	Investigator's Brochure
ICF	Informed consent form
ICH	International Conference on Harmonization
ICU	Intensive Care Unit
IDE	Investigational Device Exemption
IEC	Independent Ethics Committee
IMT	Immunomodulatory therapy
IND	Investigational New Drug Application
IP	Investigational product
IRB	Institutional Review Board

MAA-201 VERSION 2.0

ITI	Immune tolerance induction IV intravenous
ITT	Intention-To-Treat
IV	Intravenous
LDL	Low-density lipoprotein
LLN	Lower limit of normal
MarzAA	Marzeptacog alpha (activated)
MedDRA	Medical Dictionary for Regulatory Activities
Min	Minute
MOP	Manual of Procedures
NCT	National Clinical Trial
NDA	New Drug Application
NIH	National Institutes of Health
OHRP	Office for Human Research Protections
OTC	Over-the-counter
PC	Peak concentration
PCC	Prothrombin complex concentrates
PD	Pharmacodynamics
PE	Pulmonary embolism
PI	Principal Investigator
PK	Pharmacokinetics
PRO	Patient-reported outcome
PT	Prothrombin time
QA	Quality Assurance
QC	Quality Control
r	Recombinant
rFIX	Recombinant factor IX
rFVIIa	Recombinant activated factor VIIa
RNA	Ribonucleic acid
SAE	Serious adverse event
SAP	Statistical Analysis Plan
SC	Subcutaneous
SNP	Single nucleotide polymorphisms

MAA-201 VERSION 2.0

SOA	Schedule of Activities
SOC	System Organ Class
SOP	Standard Operating Procedure
TEAE	Treatment-emergent adverse event
TAT	Thrombin-antithrombin complexes
TBIL	Total bilirubin level
TE	Thromboembolic event
TGA	Therapeutic Goods Administration
TGT	Thrombin generation time
ULN	Upper limit of normal
UP	Unanticipated Problem
US	United States
VAS	Visual analogue scale

1. PROTOCOL SUMMARY

1.1 SYNOPSIS

Title of Study: Phase 2 study to evaluate the pharmacokinetics, bioavailability, pharmacodynamics, efficacy and safety of a daily subcutaneous treatment regimen with marzeptacog alfa (activated) for bleeding prophylaxis in adult subjects with hemophilia A and B with an inhibitor

Primary Objective: To evaluate the efficacy and safety of a daily subcutaneous (SC) treatment regimen with MarzAA for bleeding prophylaxis in adult subjects with Hemophilia A and B with an inhibitor.

Secondary Objectives:

- To determine the pharmacokinetics (PK) of SC MarzAA.
- To determine the bioavailability of MarzAA when given via SC.
- To determine the pharmacodynamics (PD) of SC MarzAA.
- To evaluate and compare the levels of thrombogenicity markers following administration of a SC dose of 30 µg /kg MarzAA with the IV dose of 18 µg/kg MarzAA.
- To evaluate for evidence of the development of antibodies to MarzAA, wild type recombinant factor VIIa (wt-rFVIIa), and/or wt-FVII, and to determine if these are neutralizing antibodies.
- To determine the annualized bleeding rate (ABR) during MarzAA treatment compared to the rate of historic on-demand treatments.

Study Population: Twelve male subjects, aged 18 or older, with confirmed diagnosis of severe congenital hemophilia A or B with an inhibitor and history of frequent spontaneous bleeding episodes (historical annualized bleeding rate [ABR] of ≥ 12).

Phase of Development: Phase 2

Description of Sites: Multinational study conducted at up to approximately 10 centers.

Study Duration: Approximately 1 year

Participant Duration: The minimum duration of treatment for each subject is approximately 2 months (if no dose escalation is required) and the maximum duration is approximately 7 months (if three dose escalations are required).

Screening: Up to 4 weeks

Part 1a: 24 hours (single IV dosing and PK/PD/Safety testing)

Part 1b: 48 hours (single SC dosing and PK/PD/safety testing)

Part 2: Up to 197 days of daily SC dosing

Note: Where interruptions to study drug dosing days are observed, study duration may be extended to incorporate full dosing schedule.

Follow-up: Two weeks after last dose for PK/PD/safety follow-up and then approximately and additional 2 weeks follow-up to study completion.

MAA-201 VERSION 2.0

Subjects must have no spontaneous bleeding for 50 days at any dose level and at least 50 exposure days and 30 days post-treatment follow-up to complete the study. Subjects escalating to 120 µg/kg will continue treatment for 50 exposure days to determine the bleed rate.

Study Methodology

This multi-center, open-label Phase 2 study will evaluate the PK, bioavailability, PD, efficacy and safety of a daily SC treatment regimen with MarzAA for bleeding prophylaxis in adult subjects with hemophilia A and B with an inhibitor. The study will enroll and dose, both intravenously and subcutaneously, a total of 12 adult male subjects with severe congenital hemophilia A or B with an inhibitor, and history of frequent bleeding episodes during the 6 months prior to enrollment, as per the individual's bleeding and treatment records.

At the screening visit and prior to any study procedures, subjects will sign an informed consent form (ICF). Eligibility to participate in the study will be determined by inclusion and exclusion criteria elicited from medical history, hemophilia history, physical examination, laboratory assessments and an electrocardiogram (ECG). At screening, subjects will be provided with a diary in which they will be instructed to record any adverse events (AEs) and concomitant medication. The screening period duration may be up to 4 weeks.

After the first IV dose of MarzAA, subjects will record daily study drug administration (to assess compliance), injection site assessment, any AEs they may experience, and bleeding episodes (location, inciting event if not spontaneous, and treatment administered), and patient reported outcome (PRO) scales.

Once a subject is enrolled into the trial, the study will be conducted in two phases consisting of three parts (occurring consecutively):

Part 1: Single dose administration

Part 1a (24 hours): Single IV administration of MarzAA at 18 µg /kg with assessment of PK, PD, and safety for 24 hours post-dose.

Part 1b (48 hours): Single SC administration of MarzAA at 30 µg /kg with assessment of PK, PD, and safety for 48 hours post-dose

Part 2: Daily SC administration

Daily SC administration of MarzAA at 30 µg /kg with assessment of PK, PD, and safety at designated days for 50 treatment days.

If dose escalation is required because of a spontaneous bleeding episode, then assessments of PK, PD, and safety will be at designated days for an additional 50 treatment days.

MAA-201 VERSION 2.0

Study Treatment and Assessments:

Part 1a: Single IV administration

Each subject will receive an IV dose of 18 µg/kg MarZAA. PK, PD, and safety assessments will be collected pre-dose and post-dose at 5 and 30 minutes and at Hour 1, 3, 6, 9, 12, and 24.

Part 1b: Single SC administration

After the initial 24 hours, the same subject will receive a SC dose of 30 µg/kg MarZAA. PK, PD, and safety assessments will be done at pre-dose and repeated at Hour 3, 5, 7, 9, 12, 24, 30, and 48. At any time during this period, subjects will be trained by appropriate study staff to self-administer a SC injection.

Part 2: Daily SC administration

At Day 1 of daily SC dosing, subjects will begin their self-administered dosing regimen. MarZAA will be self-administered by subjects daily (at approximately the same time every day), starting with a SC dose of 30 µg/kg MarZAA. At each dose, subjects will record the day and time of the SC injections in their diary. If a spontaneous bleeding episode (defined as one that is precipitated by normal activities of daily living [ADL]) occurs before the fifth daily dose, subjects will continue at the current dosing level. If a spontaneous bleeding episode occurs after the fifth daily dose, the MarZAA dose will be escalated to the next dose level. Three dose escalations are allowed during part 2: 60, 90, and 120 µg/kg (maximum dose). At each dose level escalation, safety and PK/PD will be monitored to ensure that dose escalation to a higher dose level is appropriate. If a subject requires a third dose escalation to the fourth dose level, then they will continue treatment with that dose for 50 days and complete the study, regardless if a spontaneous bleeding episode occurs during the highest treatment dose level.

Treatment of a spontaneous bleeding episode: Subjects will use their current bypass regimen for any spontaneous or traumatic bleed that occurs while on study drug. If treatment for a breakthrough bleeding episode is needed, then subjects will contact the clinical investigative team immediately to report the event; treatment dose administered; and determine follow-up plans for that event, including to arrange for a blood specimen to be drawn (if feasible) before further administration of either study drug or bypassing agent used for treatment. This information will also be recorded in the subjects' diary.

Dose interruption and surgery: Daily SC study injections will be interrupted, as needed, if there is a need for a surgical procedure; an event requiring extended (>48 hours) hospitalization; a thrombotic event; clinical evidence of inhibitor formation; or laboratory results suggesting an antibody may be developing.

Measurements:

MarZAA antigen and activity levels, as well as coagulation parameters, will be measured during Part 2 of the study at Day 1 (At pre-dose and Hour 7 post-dose, Day 3 (Pre-dose), Day 5 (Pre-dose), Day 7 (Pre-dose and Post-dose Hour 7).

MAA-201 VERSION 2.0

If no spontaneous bleeding occurs at the first dose level in part 2 of the study, trough antigen and activity, as well as coagulation parameters, will be measured on days 14, 21, 28, and 50 after starting their dosing regimen.

If spontaneous bleeding occurs after the fifth daily dose at any dose level, MarzAA antigen and activity levels will be measured within 6 hours of the spontaneous bleed (if feasible). Specimens for coagulation and immunogenicity testing will also be drawn.

Once it is determined to escalate to the next dose level, a pre-dose and Hour 7 post-dose specimen, will be drawn for PK, coagulation, and thrombogenicity markers on Day 7 *after* the dose has been escalated to estimate the *new* trough and peak concentrations (PCs) and PD. MarzAA antigen and activity levels, as well as coagulation parameters, will then be measured (pre-dose) at Day 14, 21, 28, and 50 after dose escalation.

Immunogenicity assays: Specimens for immunogenicity testing (antibody to MarzAA, neutralizing activity, cross reactivity) will be drawn at screening, Part 1a pre-dose, Part 1b pre-dose, and during part 2 pre-dose on Day 1, 7, 14, 21, 28, and 42, and then every two weeks until end of study.

Number of planned subjects: 12

Trial population:

Inclusion criteria:

1. Confirmed diagnosis of severe congenital hemophilia A or B with an inhibitor.
2. History of frequent spontaneous bleeding episodes (historical annualized bleeding rate [ABR] of ≥ 12).
3. Male, age 18 or older.
4. Agreement to use highly effective birth control throughout the study.
5. Affirmation of informed consent with signature confirmation before any trial-related activities. (Trial related activities are any procedure that would not have been performed during normal clinical management of the subject).
6. Stated willingness to comply with all study procedures and availability for the duration of the study.

Exclusion criteria:

1. Receiving prophylaxis treatment.
2. Previous participation in a trial involving Subcutaneous Administration of rFVIIa (Novo Seven or MOD-5014) or any trial using a modified rFVIIa such as: NN1731 or BAY86-6150. Prior participation in a trial of LR769 or rFVIIa-FP (CSL689) is permissible.
3. Previous participation in and subsequent treatment in a clinical trial within the previous 30 days or 3-half-lives or absence of clinical effect, whichever is longer.
4. Known positive antibody to FVII or FVIIa detected by central laboratory at screening.
5. History of clinically relevant coagulation disorders other than congenital hemophilia A or B.
6. Platelet count $< 100,000$ based on screening laboratory assessments.

MAA-201 VERSION 2.0

7. Advanced atherosclerotic disease (i.e. known history of coronary artery disease (CAD), ischemic stroke, etc.), or known deep venous thrombosis (DVT) or considered to be at a high risk of venous thromboembolic event (VTE) as judged by the Investigator.
8. Known or suspected allergy to trial product or related products.
9. Absolute cluster of differentiation 4 (CD4) count <200 cells/ μ L.
10. Receiving immunomodulatory therapy (IMT).
11. Compromised hepatic or renal function:
 - o Alanine aminotransferase (ALT) and aspartate aminotransferase (AST) levels \geq 5 times the upper limit of normal (ULN)
 - o Total bilirubin level (TBIL) \geq 2 mg/dL (>35 μ mol/L) unless there is a known history of Gilbert's syndrome (GS)
 - o Serum albumin \leq the lower limit of normal (LLN)
 - o Serum creatinine (Cr) level >1.25 x ULN
12. Inability or medical, psychosocial, or familial issues that might prevent full participation and cooperation with the procedures and requirements of the clinical trial as determined by the potential subject and physician investigator.

Investigational product, dose, and mode of administration:

Investigational Product: Recombinant Factor VII variant, Marzeptacog alfa (activated) [MarzAA]

Dosage and mode of administration: Single IV dose at 18 μ g/kg and then an initial SC doses at 30 μ g/kg. Dose levels may increase to 60, 90, or 120 μ g/kg, as required

Reference therapy: None

Concomitant Medications: In the event of spontaneous or traumatic bleeding, treatment for a bleeding episode will be permitted using the subject's current treatment regimen which could be FEIBA[®] (anti-inhibitor coagulant complex [AICC]), NovoSeven[®] (recombinant wild-type factor VII activated [wt-rFVIIa]), or a high dose regimen utilizing a FVIII or FIX product.

Efficacy and Safety Evaluations

Primary endpoints:

- Annualized bleed (spontaneous and total) rate (ABR) during Part 2 when on final MarzAA dose level versus recorded historical ABR.

Secondary endpoints:

- Occurrence of breakthrough bleeds requiring escalation to higher dose level.
- Safety parameters: Occurrence of clinical thrombotic event not attributable to another cause, and occurrence of antibody formation resulting in a decreased endogenous level of FVII or FVIIa.
- Change in coagulation parameters (prothrombin time [PT], activated partial thromboplastin time [aPTT], fibrinogen, MarzAA antigen and activity levels, and thrombin generation time [TGT]) from pre-dose.
- Occurrence of an antibody response to MarzAA and whether it is inhibitory and cross-reactive to wild-type recombinant FVIIa (wt-rFVIIa) or wt-FVII.

[figure not shown]
MAA-201 VERSION 2.0

• Clinically significant levels of thrombogenicity markers resulting from daily SC administration of MarzAA.• Feasibility and ease of use of daily SC self-administration by subject as measured by compliance with treatment.

Exploratory endpoints
 
• Identification of biomarker(s) such as antigen levels, activity levels, or global thrombosis assay evaluation that can be used to predict or correlate with a subject's lack of spontaneous bleeding.• Identification of biomarker(s) such as D-dimer, F1+2, or a functional assay of the FVIIa activity that will identify or predict clinical thrombogenicity with the daily SC administration of MarzAA.• Identification of biomarker(s) such as D-dimer, F1+2, or a functional assay of the FVIIa activity that will identify or predict clinical thrombogenicity of daily SC administration of MarzAA when use of rescue medication is required.• PRO measures: European Quality of Life-5 Dimensions(EQ-5D), Visual analogue scale (VAS); Hemophilia A quality of life questionnaire(Haem-A-QoL); Hemophilia Activities List (HAL)

Statistics
 
Primary Analysis Plan:
 
Standard pharmacokinetic parameters, such as terminal half-life, AUC_{0-t}, clearance, mean residence time and volume of distribution will be calculated. In addition, the bioavailability of the SC administration will be computed. Descriptive statistics for these parameters will be reported. The number of subjects requiring dose escalation will be reported.
 
The analysis of the primary endpoint (ABR) of the final dose used to treat a subject will be based on the evaluation of the ABR of MarzAA compared to a rate for on-demand therapy. The latter is assumed to be 12, ie, 1 bleed per month, as our null hypothesis (H₀). The comparison of the actual ABR for MarzAA either pooled across all doses used or evaluated at the highest dose for an individual will be compared to this null hypothesized value using the one-sample test for a Poisson rate (using an exact calculation of the p-value). Because this will be a one-tailed test (the alternative hypothesis [H₁] is the ABR for MarzAA will be < 12), a one-tailed 2.5% significance level will be used.

Rationale for Number of Subjects:
 
With a total of 12 subjects and assuming a null hypothesis of an ABR of 12, then the demonstration of a reduction to an ABR of 6 or less with a one-tailed 2.5% significance level would be accomplished with near 100% power using a one sample Poisson test of the null hypothesis. Even if only 6 subjects were available to be pooled for this analysis, the power would still be in excess of 99%.

Name of sponsor: Catalyst Biosciences

MAA-201 VERSION 2.0

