
Treatment of inhibitor patients with wt-rFVIIa or with APCCs has limitations with regard to efficacy, safety, and/or convenience²⁷⁻²⁹, and therefore presents opportunities for development of improved or alternative biotherapeutics to satisfy an unmet medical need in this patient population. Efficacy of wt-rFVIIa or APCCs in patients with inhibitors is suboptimal in terms of ability to control bleeds and with regard to duration of action. These therapies fall short of the efficacy achieved with conventional factor replacement therapies in patients without inhibitors.^{10,30,31} Because efficacy is suboptimal with either of the currently licensed products, elective surgical procedures may be deferred for patients with inhibitors who may need such procedures.³² Pathogen transmission, thromboembolic

MAA-201 VERSION 2.0

events, hypersensitivity and anamnestic response resulting in an increase in inhibitory antibody titers have been the main safety concerns when treating patients with hemophilia with inhibitors.^{20,25} Thrombotic events in association with NovoSeven® treatment in hemophilia patients with inhibitors have been reported in up to 4% of patients.^{20,33-35} Reported incidence of thrombotic events in association with FEIBA® use ranges from 4-8.24/100,000 infusions.^{25,36-38} NovoSeven® is not approved for prophylaxis and its use for that purpose is not generally feasible for many reasons, including short duration of action that precludes administration schedules practical for routine use.^{20,39} The percent reduction in annual bleed rate during prophylaxis of hemophilia patients with inhibitors with FEIBA®⁴⁰ is less than that reported for factor replacement therapy in hemophilia patients without inhibitors.⁴¹ FEIBA® also contains small amounts of FVIII and has the potential to boost inhibitor titers in hemophilia A patients with inhibitors.⁴

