6.1.2.1 Guidelines for Dose Escalation

An escalation to the next dose level is required if a spontaneous bleeding event occurs after the fifth daily dose on a dose level. A dose escalation will not occur if the subject is on the maximum dose level of 120 µg/kg. A spontaneous bleeding episode is defined as one that is precipitated by normal activities of daily living (ADL). Subjects will use their current bypass regimen for any spontaneous or traumatic bleed that occurs while on study drug.

Three dose escalations are allowed during Part 2: 60, 90, and 120 µg/kg (maximum dose).

Safety parameters and PK/PD assessments at each dose level will be monitored to ensure that dose escalation to a higher dose level is appropriate.

The spontaneous bleeding episode must be reported to the clinical team immediately and determination of a dose escalation will be made on review of available clinical information related to the spontaneous bleeding episode and may require subsequent treatment and laboratory data, including available results from the PK/PD/safety assessments.

A decision to proceed with dose escalation will be made by the principal investigator in agreement with personnel who have Sponsor, or designee, medical oversight responsibility.

If there is disagreement amongst any of those individuals, the decision will be reviewed on an urgent basis by an independent Medical Consultant for Safety Oversight.

MAA-201 VERSION 2.0

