9.4.3 Analysis of the Secondary Endpoint(s)

Study drug exposure and compliance will be provided for both phases, and by treatment group for the Treatment Phase.

The following parameters will be documented:

MAA-201 VERSION 2.0

- Occurrence of clinical thrombotic event not attributable to another cause, and occurrence of antibody formation resulting in a decreased endogenous level of FVII or FVIIa.
- Change in coagulation parameters (PT, aPTT, fibrinogen, MarzAA antigen and activity levels, and TGT) from pre-dose.
- Occurrence of an antibody response to MarzAA and whether it is inhibitory and cross-reactive to wt-rFVIIa or wt-FVII.
- Clinically significant levels of thrombogenicity markers resulting from daily SC administration of MarzAA

The frequencies of these events will be summarized as proportions and counts.

Protocol deviations will be listed. All major protocol deviations (in particular those regarding entry criteria) will be summarized in the study report.

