### 8.2.2 Analysis of Occurrence of Clinical Thrombotic Event

The following categories will be summarized using ITT and modified ITT population:

- the number and percentage of subjects with thrombotic event (1 or more events)
- the number and percentage of subjects with one thrombotic event
- the number and percentage of subjects with two thrombotic events
- the number and percentage of subjects with three thrombotic events

The data will be listed.

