**Version 2.0**

**Syneos Health #1009647**

## **14 CHANGE FROM ANALYSIS PLANNED IN PROTOCOL**

1. Protocol primary efficacy endpoint stated the Poisson analysis will be performed using StatXact 11. However, SAS 9.4 will be used for the exact analyses as specified in this SAP.

Statistical Analysis Plan

Catalyst Biosciences, Inc. Protocol # MAA-201

Version 2.0

Syneos Health #1009647

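### The thrombotic safety endpoint is limited to events not put down to another cause, an undefined filter that the SAP table reporting it does not carry

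*Protocol*

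**What the plan says.** The endpoint is worded the same way in Protocol 1.1 (secondary endpoints), 9.1 and 9.4.3 and in SAP 4.2: "Occurrence of clinical thrombotic event not attributable to another cause". Protocol 9.4.3 lists it among the parameters to be documented and adds: "The frequencies of these events will be summarized as proportions and counts". As the protocol is written, then, the summarised frequency is that of the restricted event.

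SAP 8.2.2, the analysis section for this endpoint, drops the restriction. Its first row is "the number and percentage of subjects with thrombotic event (1 or more events", followed by rows for one, two and three events, in the ITT and modified ITT populations, with a listing. SAP section 14 declares one change from the protocol, about software: "Protocol primary efficacy endpoint stated the Poisson analysis will be performed using StatXact 11". SAP 9.6 and 10.7 add only the PK and PD populations.

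On rescue, Protocol 6.1.2.1 says: "Subjects will use their current bypass regimen for any spontaneous or traumatic bleed that occurs while on study drug". The synopsis names FEIBA, NovoSeven or high-dose FVIII or FIX as possible regimens. Protocol 2.2 reports thrombotic events with both bypassing agents; for NovoSeven they "have been reported in up to 4% of patients". An exploratory endpoint seeks biomarkers that will identify or "predict clinical thrombogenicity of daily SC administration of MarzAA when use of rescue medication is required".

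**The concern.** The qualifier makes membership of a safety endpoint depend on a causal judgement that the documents leave open. The judgement would be made by people who know the treatment (Protocol 6.3), with no control arm to calibrate it. The independent consultant's role in Protocol 10.1.6 covers dose escalation and de-escalation, not the cause of thrombotic events.

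Bypassing-agent rescue supplies a plausible alternative cause, because the protocol itself associates these agents with thrombosis. A thrombosis that follows rescue could be assigned to the rescue agent and so fall outside the endpoint, while the exploratory aim on thrombogenicity under rescue is about that same setting.

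The SAP does not settle the matter. Section 8.2.2 sits under the heading for secondary endpoints, so a programmer could carry the SAP 4.2 definition into the table, or could take 8.2.2 as written and count everything. Both readings are defensible and they can give different results. This matters because SAP 8.2.2 is the only planned table that adds thrombotic events together. SAP 12.3 has no table for adverse events of special interest and reports by system organ class and preferred term, so a myocardial infarction, a venous thrombosis, a pulmonary embolism and a stroke would appear on separate lines.

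**Working it through.** **No stated figure to reproduce.** The documents give no rate, threshold, power or sample size for the thrombotic endpoint. What can be checked is whether the definitions agree and what one event is worth.

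**Definitions side by side**

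| Place | Limited by attribution? |
|---|---|
| Protocol 1.1, 9.1, 9.4.3 | Yes |
| SAP 4.2 | Yes |
| SAP 8.2.2 (pooled table) | No |
| Protocol 8.5.7 (thromboembolic events of special interest) | No |
| Protocol 8.5.4 (AE recording), SAP 12.3 (all TEAEs) | No |

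The nearest standard for causality is Protocol 8.5.3.2, which grades each AE as related or not related; it is not linked to the endpoint's wording. Unreported relationships are also handled in opposite ways: Protocol 9.4.4 counts them as not related, SAP 12.3 as related.

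**What one event is worth.** Input: 12 planned subjects (Protocol 9.2). Exact (Clopper-Pearson) 95% limits:

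- Event left out, 0/12: upper limit = 1 − 0.025^(1/12) = 0.265. Result: 0%, 95% CI 0% to 26.5%.
- Event counted, 1/12 = 8.3%: lower limit = 1 − 0.975^(1/12) = 0.002; the upper limit solves (1−p)^12 + 12p(1−p)^11 = 0.025, giving p = 0.385. Result: 95% CI 0.2% to 38.5%.
- Two events counted, 2/12 = 16.7%: 95% CI 2.1% to 48.4%, against 0/12 if both are left out.

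**How often rescue could arise.** Assumptions, none stated as such in the documents: constant Poisson bleeding, 50 days per subject, every bleed treated. P(at least one bleed) = 1 − exp(−ABR × 50/365.25).

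| ABR on treatment | P(at least one bleed) | Expected subjects of 12 |
|---|---|---|
| 1 | 13% | 1.5 |
| 3 | 34% | 4.0 |
| 6 | 56% | 6.7 |
| 12 | 81% | 9.7 |

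ABR 12 and 6 are the null and alternative values in Protocol 9.2; 1 and 3 are added for range.

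**Illustration in days.** Expected bleeds in 12 × 50 = 600 subject-days are 6 × 12 × 50/365 = 9.9 and 12 × 12 × 50/365 = 19.7. If each treated bleed opened a window of 2 to 7 days (an assumption with no source in the documents), the share of days would run from 9.9 × 2/600 = 3.3% to 19.7 × 7/600 = 23%. This is a share of days on which the question could arise, not a share of events removed.

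**The case against.** The strongest reply is that the plan already does most of what is wanted. SAP 8.2.2 as worded counts every thrombotic event and lists the data. Protocol 8.5.4 records all adverse events whatever their relationship, 8.5.7 makes thromboembolic events of special interest without an attribution condition, and SAP 12.3 tabulates all TEAEs and splits them by relationship. A post-rescue thrombosis would not vanish from the trial's safety data. Protocol 8.5.3.2 also requires the study product always to be under suspicion, accepts a temporal link as enough for relatedness, and asks that an alternative etiology be established. Under daily dosing, many post-rescue events would meet the temporal criterion.

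All of that stands, and it limits the point. A reader might infer four stronger things that the documents do not support:

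- **That the reported rate is certainly biased downward.** That depends on whether the qualifier is applied in SAP 8.2.2, which is unresolved, and on how causes would be assigned.
- **That this is the trial's main safety endpoint.** It is one item in a secondary bullet, although safety is part of the primary objective.
- **That the time around rescue carries the highest risk.** No passage says so or gives a thrombosis rate for it. Dosing may be interrupted for a bleed (6.1.2.3), and an escalated dose starts after the bleed resolves (8.2.6), so overlap is not automatic.
- **That one reclassified event would change the trial's conclusion.** No test, threshold or stopping rule is attached to this endpoint, and the two intervals overlap widely.

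The frequency figures are also only rough. Completion at the first three dose levels requires 50 days with no spontaneous bleed (4.2), escalated subjects are treated for longer than 50 days, and not every rescue need be a bypassing agent.

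The reply does not remove the contradiction between SAP 4.2 and 8.2.2, or the lack of any definition of the qualifier. Nor do the TEAE tables replace a pooled count.

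**Conclusion.** The point holds as an undefined, open-label attribution filter in the endpoint and a mismatch with the table that reports it. Four places restrict the endpoint, SAP 8.2.2 does not, and no change is declared. If the restriction is applied, a thrombosis after bypassing-agent rescue could be missing from the only pooled thrombotic-event table while still appearing in the AE listings and TEAE tables.

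In size, one such event separates a reported 8.3% from 0%. This takes the planned 12 subjects as the denominator; replacement under Protocol 7.2 could raise the number dosed and lower the percentage slightly. Since the documents give no expected event count, the calculation shows what an event is worth, not how many would be lost.

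**What to change.** 1. Delete the qualifier from the endpoint in Protocol 1.1, 9.1 and 9.4.3 and in SAP 4.2, so that they agree with SAP 8.2.2.
2. State in SAP 8.2.2 that every clinical thrombotic event is counted whatever its attribution, including the events named in Protocol 8.5.7.
3. Add to the SAP 8.2.2 listing the assigned relationship and the time since the last bypassing-agent dose, and show them as a supportive breakdown. Onset and relationship are recorded under Protocol 8.5.4, and dated hemostatic treatment under 8.1, so no new data are needed.

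The cost is one phrase removed in four places, one sentence and two listing columns. No treatment, rescue or stopping rule is affected. The downside is that the reported thrombotic rate may be slightly less favourable.
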